Population: 10,449 patients aged 16-35 years in CPRD with TASD and two years follow up.

WP1: Internal and external validation of shoulder dislocation coding and treatments within a routinely collected dataset (CPRD).

WP2: Propensity score-matched cohort study using linked CPRD and HES. All events and outcomes will be collected using a pre-agreed list of READ CODES (CPRD) and OPCS 4.7 CODES (HES).

Exclusions: Surgery after more than one dislocation; instability treated with a rotator cuff repair or fracture surgery.

Intervention: Surgical repair within 6 months of first time T ASD.

Control: non-surgical intervention.

Outcomes: Rate of re-dislocation, identified by codes in CPRD for 2 years after either treatment.

Sample size: 3065 with 656 expected total number of re-dislocations (90% power, 5% significance).

Statistical analysis: Propensity scores, Cox regression modelling and Rosenbaum bounds sensitivity analysis for *Surgical versus non-surgical intervention on re-dislocation*. Multiple imputation methods, survival models and fractional polynomials for *Predictors of recurrent dislocations*.

C. Objectives, Specific Aims and Rationale

Aim 1. To study the association between surgical treatment (compared to no surgery) and recurrence rates following a first episode of traumatic anterior shoulder dislocation (T ASD) amongst young adults. **Aim 2.** To identify clinical predictors of further recurrent dislocations in young adults with traumatic anterior shoulder dislocation stratified by surgery and no surgery.

Objectives: Following the HTA commissioning brief, we plan to use routinely collected observational datasets (Clinical Practice Research Datalink (CPRD) and Hospital Episodes Statistics (HES)) to answer the research questions above. The size of routinely collected data in UK primary care (CPRD) and secondary care (HES) offers rapid observational data to uncertainties about treatments in an affordable and generalisable manner. We have planned a propensity score-matched cohort study, with the intention to minimise confounding. Propensity score matching is considered one of the best methods available to approximate to any results obtained from randomised controlled trials. To ensure further value for money and to confirm the ability of these datasets to answer this very specific commissioned question, we plan a two stage approach through Work Packages 1 and 2.

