Main study (WP2): The main study (WP2) will be a population based propensity score-matched cohort study using CPRD and HES collected datasets. The cohort of participants in this study will be young adults (aged 16–35 years) with traumatic anterior shoulder dislocation (T ASD) with at least 2 years data entry in CPRD before the their first shoulder dislocation code and at 2 years follow up from their first dislocation code entry in CPRD. All events and outcomes will be collected using a pre-agreed validated list of READ CODES (CPRD) and OPCS 4.7 CODES (HES). These codes are listed in the appendices and have already been identified. They will be further validated and informed by WP1. The first read code entry in CPRD for shoulder dislocation will be defined as the ‘first dislocation’. These codes will then be routinely linked to patients and to HES.

The ***Intervention group*** will be patients in CPRD with first time T ASD who underwent shoulder stabilisation surgery after their first dislocation (early surgical repair in this NHS context will mean ‘a decision to treat surgically after the first T ASD’ and receiving surgery within 6 months). This means linking HES data to CPRD data in such a way that a HES surgical OPCS 4.7 code is seen to occur after a single first dislocation code in CPRD (without further dislocation codes) before that surgical date. The timelines between first dislocation codes and OPCS 4.7 codes will be recorded. The ***Control group***. While the most desirable control group would be physiotherapy, it is possible that WP1 will reveal that free text notes and referral codes on physiotherapy will be lacking and not reliable. If this is the case then conservative care will be defined as ‘non surgical intervention’ with no linked OPCS 4.7 surgical shoulder codes producing a control cohort of patients whose first time shoulder dislocation has been treated non-operatively. If however free text entries and referral codes for physiotherapy are reliably present in CPRD then conservative care will be physiotherapy identified by physiotherapy referral codes after a first time T ASD code. Any subsequent dislocation codes or OPCS 4.7 surgery code will be recorded.

This project was funded by the National Institute for Health Research Health Technology Assessment (project number 14/160/01).

The views and opinions expressed therein are those of the authors and do not necessarily reflect those of the HTA, NIHR, NHS or the Department of Health.

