The ***Intervention group*** will be patients in CPRD with first time T ASD who underwent shoulder stabilisation surgery after their first dislocation (early surgical repair in this NHS context will mean 'a decision to treat surgically after the first T ASD' and receiving surgery within 6 months). This means linking HES data to CPRD data in such a way that a HES surgical OPCS 4.7 code is seen to occur after a single first dislocation code in CPRD (without further dislocation codes) before that surgical date. The timelines between first dislocation codes and OPCS 4.7 codes will be recorded. The ***Control group***. While the most desirable control group would be physiotherapy, it is possible that WP1 will reveal that free text notes and referral codes on physiotherapy will be lacking and not reliable. If this is the case then conservative care will be defined as 'non surgical intervention' with no linked OPCS 4.7 surgical shoulder codes producing a control cohort of patients whose first time shoulder dislocation has been treated non-operatively. If however free text entries and referral codes for physiotherapy are reliably present in CPRD then conservative care will be physiotherapy identified by physiotherapy referral codes after a first time T ASD code. Any subsequent dislocation codes or OPCS 4.7 surgery code will be recorded.

K. Exposures, Outcomes and Covariates

As part of this application, we have performed a consensus survey of specialist shoulder surgeons and shoulder physiotherapists who are all members of the British Elbow and Shoulder Society. Saturation point and a list of predictors was reached rapidly and this list is tabulated in Appendix E and highlights the risk factors (and covariates) deemed most important. It is unlikely that all of these will be available from routinely collected national datasets but our study design will allow us to confirm through WP1 those factors that are reliably collected and that can be used for full analysis in WP2.

L. Data/ Statistical analysis

The association of surgical versus non-surgical intervention on subsequent re-dislocation within 2-years. The primary outcome of interest is the time from a first time traumatic anterior dislocation to subsequent re-dislocation within 2-years. The exposure of interest is whether or not a patient received shoulder surgery. In randomized controlled trials each person has

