3.	Do MRI or X-ray imaging reports confirm a diagnosis of traumatic dislocation by mentioning the presence of Hill Sachs, Bankart lesion, labral tear, labral detachment, dislocation, relocation, bony Bankart?	(If YES go to Q5)	(If NO go to Q4)

This project was funded by the National Institute for Health Research Health Technology Assessment (project number 14/160/01).

The views and opinions expressed therein are those of the authors and do not necessarily reflect those of the HTA, NIHR, NHS or the Department of Health.

4.	Do Hospital letters from specialists or physiotherapists confirm traumatic instability or traumatic shoulder dislocation?	(If YES go to Q5)	(If NO go to Q8)
5.	Is there any record of a dislocation prior to the CPRD first registration date at your practice?	(If YES go to Q6)	(If NO go to Q6)
6.	Are there any further dislocation codes in the record during the 2 years after the first dislocation code?	(If YES go to Q6b)	(If NO go to Q6c)
6b.	If YES is it clear (for each one) that this is a further dislocation episode rather than simply a review of the problem?	(If YES go to Q7)	(If NO go to Q7)
6c.	If NO, have there been any further dislocations recorded during the following 2 years that are not electronically coded?	(If YES go to Q7)	(If NO go to Q7)
7.	Are there any physiotherapy treatment codes for 2 years after the first dislocation code?	(If YES go to Q7b)	(If NO go to Q7c)
7b.	If YES is it clear that this physio code indicates the patient received physiotherapy for their shoulder?	(If YES go to Q8)	(If NO go to Q8)
7c.	If NO, is there any documentation that the patient has received physiotherapy for their shoulder without a code being entered?	(If YES go to Q8)	(If NO go to Q8)
8.	If your specific responses to this questionnaire indicate that this patient has not had a traumatic shoulder dislocation but your reading of the notes or your knowledge of the patient suggest they might have please tick the YES box, otherwise tick the NO box.	The end – thank you	The end – thank you

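### If the physiotherapy control is used, its definition has no time window and no ordering rule, so a referral made after re-dislocation can make a patient a control

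*Protocol*

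**What the plan says.** Section J, repeated in Section F (Main study, WP2), gives two possible control groups. It states a preference and a condition: "While the most desirable control group would be physiotherapy, it is possible that WP1 will reveal" that notes and referral codes on physiotherapy are too poor to use. In that case "conservative care will be defined as 'non surgical intervention' with no linked OPCS 4.7 surgical shoulder codes" applies. If the coding is good, "conservative care will be physiotherapy identified by physiotherapy referral codes after a first time T ASD code". The section then says that later dislocation or surgery codes will be recorded. It does not say that they bar or date the physiotherapy exposure.

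The same paragraph puts two conditions on surgery. It must reflect "a decision to treat surgically after the first T ASD' and receiving surgery within 6 months", and the operation must follow a single dislocation code, "without further dislocation codes) before that surgical date".

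Section L starts the outcome clock at the first dislocation and runs it for 2 years. Its time-varying exposure reclassifies time before surgery as non-surgical. Section I excludes surgery after more than one dislocation. Aim 1 in Section C is "To study the association between surgical treatment (compared to no surgery) and recurrence rates". Section F promises an updated analysis plan between WP1 and WP2.

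**The concern.** Surgery carries a window and an ordering rule; physiotherapy carries neither. Because follow-up starts at the first dislocation, a referral dated after the outcome still meets the control definition. Entry to the control group can then be a consequence of the event being counted.

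If WP1 supports physiotherapy coding, this rule defines the comparator for the primary analysis. WP1 as designed would not reveal the problem. Appendix I asks "Are there any physiotherapy treatment codes for 2 years after the first dislocation code", which is the same period as the outcome, and then whether the code was for the shoulder. It does not ask whether the referral came before or after a further dislocation. Good coding would bring the rule into use unchanged.

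**Working it through.** **The plan's own figures.** Section G assumes 2-year re-dislocation of 25% without surgery and 20% with it, 90% power and two-sided 5%.
- HR = ln(0.80)/ln(0.75) = 0.776 (stated 0.78).
- Events: Schoenfeld, 4(1.960 + 1.282)²/(ln 0.776)², gives 652; Freedman, (1.960 + 1.282)²[(1 + 0.776)/(1 − 0.776)]², gives 659 (stated 656).
- With 10% loss spread exponentially over 2 years the mean event probability is 0.21404, and 656/0.21404 = 3065 (as stated).

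The sample size is not in question. The 25% and 0.78 serve below as yardsticks.

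**Two non-operated patients.** Neither is referred after the first dislocation. Patient A never re-dislocates and is never referred, so A has no physiotherapy code and is not a control. Patient B re-dislocates at month 10, is referred at month 11, and becomes a control with an event. Only the outcome separates them.

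**What the stated analysis repairs.** The time-varying exposure (Section L) moves only pre-surgery time. Propensity matching (Sections L and M) balances covariates at baseline, and this selection happens later. Rosenbaum bounds address an unmeasured confounder, not entry that depends on the outcome.

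**Size.** Suppose surgery has no effect and the true 2-year risk is 25% in both arms. Let
- p = share referred early, whatever the outcome;
- q = among re-dislocators not referred early, the share referred after re-dislocating;
- r = among the others not referred early, the share referred late without re-dislocation;
- s = share of re-dislocators removed by the Section I exclusion, taken as equal across referral routes.

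The protocol gives none of these; all four are assumptions. Then

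a = 0.25[p + (1 − p)q](1 − s), b = 0.75[p + (1 − p)r],

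control risk = a/(a + b), and apparent HR = ln(0.75)/ln(1 − control risk).

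| p | q | r | s | a | b | Control risk | Apparent HR |
|---|---|---|---|---|---|---|---|
| any | 0 | 0 | 0 | 0.25p | 0.75p | 25.0% | 1.00 |
| 0.6 | 0.25 | 0 | 0 | 0.175 | 0.450 | 28.0% | 0.88 |
| 0.4 | 0.5 | 0 | 0 | 0.175 | 0.300 | 36.8% | 0.63 |
| 0.6 | 0.25 | 0.1 | 0 | 0.175 | 0.480 | 26.7% | 0.93 |
| 0.5 | 0.4 | 0.1 | 0 | 0.175 | 0.4125 | 29.8% | 0.81 |
| 0.6 | 0.25 | 0.1 | 0.2 | 0.140 | 0.480 | 22.6% | 1.12 |
| 0.5 | 0.4 | 0.1 | 0.2 | 0.140 | 0.4125 | 25.3% | 0.98 |
| 0.5 | 0.4 | 0.1 | 0.4 | 0.105 | 0.4125 | 20.3% | 1.27 |

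Rows 2 and 3 set r to zero, which is the most unfavourable choice. Rows 4 and 5 relax it. With s = 0 and p 0.3 to 0.7, q 0.2 to 0.6, r 0 to 0.2, the apparent HR runs from 0.49 to 1.00. It is 1.00 whenever q = r.

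**Separating the two mechanisms.** Relative to an all-non-surgical control under the same exclusion, the physiotherapy rule multiplies the control odds by [p + (1 − p)q]/[p + (1 − p)r], whatever s is. For p = 0.5, q = 0.4, r = 0.1 this is 0.70/0.55 = 1.27. At s = 0.2 the all-non-surgical control reads 21.1% and the physiotherapy control 25.3%; at s = 0.4, 16.7% and 20.3%. The two mechanisms cancel at s = 1 − 0.55/0.70 = 0.21 in this case, and at values from 0 to 0.58 over the grid.

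**The case against.** Several points against the concern have force.

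- **Direction.** A reader might infer that controls are selected because they failed, and that surgery must look better than it is. The documents do not support that. Controls referred early are not selected on outcome. If late referral is equally common with and without re-dislocation, this route adds no bias. The Section I exclusion, read on the whole cohort, drops patients who fail and then have surgery, which lowers control risk. This stands, and it limits the claim to one route with an unknown net sign. It does not make the rule sound: an opposing bias of unknown size is not a correction.
- **Conditional branch and later plan.** The rule applies only if WP1 supports it, an updated analysis plan is promised, and a date limit on a code is the kind of detail such a plan often supplies. This lowers the urgency. But the protocol states both conditions for surgery in the same paragraph and neither for physiotherapy, and nothing says that the update will revisit the definition.
- **A more natural reading.** The sentence about recording later events suggests the order first dislocation, conservative care, further events. That may be what is meant, but an extraction that follows the words would admit patient B.
- **Choice of comparator.** A reader might conclude that no surgery must be the primary control whatever WP1 finds, since Aim 1, the Technical Summary and Section L are worded that way. That goes too far. The protocol calls physiotherapy the most desirable comparator, and restricting to physiotherapy-treated patients is a legitimate choice of question. What remains is that this branch departs from Aim 1's wording, so both results should be shown.
- **Appendix I.** The questionnaire validates coding and does not define the WP2 control group. It shows only that WP1 would not detect the ordering problem.

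**Conclusion.** The point holds in limited form. If the physiotherapy branch is used as written, control membership can depend on re-dislocation, and no stated analysis step removes that. When re-dislocators are referred late more often than others (q > r), this route raises control risk and favours surgery. Under assumed shares that allow 10% late referral without re-dislocation, a true null reads as HR 0.81 to 0.93; the wider grid gives 0.49 to 1.00. The study is sized for 0.78, so the distortion could be as large as the effect sought.

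The net bias is not determined by the document: with 20% to 40% of re-dislocators removed by the Section I exclusion, the p = 0.5 case moves from 0.81 to between 0.98 and 1.27. The figures rest on assumed referral and exclusion shares, a 25% risk in both arms, and conversion of 2-year risks to hazard ratios under proportional hazards. They illustrate the mechanism and do not forecast the result.

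**What to change.** In Sections F and J, if the physiotherapy branch is used:

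1. Count a physiotherapy code only if it is dated within the same 6-month window as surgery and before any second dislocation code.
2. Align the start of follow-up in both arms, by a landmark or by time-varying entry at the code date, and say where time before the physiotherapy code and before surgery is counted. Without this, step 1 would give controls guaranteed event-free time up to their referral.
3. Report the all-non-surgical comparison named in Aim 1 alongside. It involves no selection on referral, although it remains exposed to the exclusion of surgery after more than one dislocation.

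The cost is a few lines of protocol text, one extra date condition at extraction, and a somewhat smaller physiotherapy group. The sample-size calculation does not change.

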CPRD Internal Validation. 100 random sets of notes of patients aged 16-35 years with first time T ASD will be identified in CPRD. First time T ASD will be those patients with at least two years of data (washout period) before a first time entry read code for shoulder dislocation and with at least a further two years of follow up coding. These notes will be assessed for: use of shoulder dislocation codes for traumatic dislocation; confirming first time shoulder dislocation; confirming traumatic cause; and assessing the subsequent codes used for further events. Physiotherapy referral codes regards physiotherapy will also be assessed especially in terms of data on frequency of therapy, place of therapy (hospital or community) or type of therapy. Overall, data quality and completeness will be assessed using the GP questionnaire service (Appendix I) provided by CPRD. This questionnaire is based on the validation algorithm in Appendix H. Those risk factors that may play an important role as predictors of further re-dislocation and that are identifiable in CPRD will also be recorded. This analysis would ascertain which factors are reliably identifiable in CPRD and inform any formal analysis in WP2 regards future predictors.

Prevalence Rates (External Validation). We will compare age-gender prevalence rates of first time dislocators identified in our study with those of similar studies in other settings [7, 20]. This will externally validate GP and primary care coding of this condition. This external validation study will itself provide first time age and gender prevalence data on traumatic anterior shoulder instability in the UK.

During work package 1, if the analysis of the notes indicates that first time dislocation coding and recurrent dislocation coding is poor then the study cannot proceed and will be STOPPED (Red Light). To quantify this if during our review of coding and free text entries on patients with first time T ASD, if the positive predictive value of CPRD codes is $\geq 75\%$ (% recorded according to READ/OXMIS codes that are confirmed in the free text search) then we will continue to Stage 2 (Green Light). We would also take this opportunity to estimate the sensitivity of T ASD coding by using the algorithm on CPRD codes of alternative coding diagnose to include, but not limited to, shoulder pain, rotator cuff disorder, shoulder OA.

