Matched surgical patients and their non-surgical controls will then be included in a Cox regression survival model to describe the association between receipt of surgery and time to subsequent dislocation within 2-years. The model is stratified on matched sets, to allow for the correlation between matched pairs of surgical patients and controls. As clustering exists within the data (patients nested within GP practices), a multilevel survival model will be fitted by extending the Cox regression model to include a frailty term with a Gaussian distribution[8]. This will allow adjustment for evidence of unexplained variation across GP practices. To assess the potential effect of unmeasured confounders we will conduct a Rosenbaum bounds sensitivity analysis[9]. This provides an estimate of the magnitude of hidden bias that would have to be present to explain the associations actually observed. The proportional hazards assumption will be assessed using Schoenfeld's residuals. Kaplan-Meier plots will be used to estimate the probability of survival up to 2-years in surgical and non-surgical groups.

Identifying predictors of recurrent dislocations

Using the CPRD-HES linked dataset we will develop a prediction model to identify patients at increased risk of subsequent re-dislocation. Potential risk factors will include all those described above. The cumulative effect of missing data in several variables often leads to exclusion of a substantial proportion of the original sample, causing a loss of precision and power. To overcome this bias we will use multiple imputation methods, which allows for the uncertainty about missing data by creating several plausible imputed datasets and appropriately combining their results [10, 11].

Survival models (Cox regression) will be used to identify risk factors associated with time to re-dislocation. Backward selection methods will be used to identify risk factors and shrinkage methods applied to adjust for over fitting. Continuous predictors will be examined using fractional polynomials and clinically plausible interaction terms will be tested for inclusion (specifically whether the predictors differ in the surgical and non-surgical intervention groups). For internal validation of the model we will use a combination of multiple imputation and bootstrapping[12-14].

Performance of the model will be assessed in terms of calibration and discrimination[11, 23]

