APPENDIX E

Table of Expert Consensus List of Risk Factors.

Risk factors for re-dislocation after first dislocation	Risk factors for re- dislocation after surgery
Age	Age
Gender	Gender
UK Region	UK Region
Deprivation Scores	Deprivation Scores
Glenoid and / or Humeral Bone loss	Glenoid and / or Humeral Bone loss
Mechanism of injury	Number of dislocations pre-surgical repair
Rotator cuff tears	Time between first dislocation and surgery
Imaging findings	Anterior apprehension
Anterior apprehension	Occupation
Occupation	Sport type and level
Sport type and level	Operation type
Neurological injury	Laxity/Beighton Score
Laxity/Beighton Score	Insufficient physio / rehab after surgery
Insufficient physio / rehab after first dislocation	Time for return to sports
Young Rugby player under 20	Number of anchors used at surgery
Time at return to sports	Incorrect positioning of anchors
Post dislocation immobilisation	Not addressing capsular laxity at surgery
	Previous lower limb or back injury

This project was funded by the National Institute for Health Research Health Technology Assessment (project number 14/160/01).

The views and opinions expressed therein are those of the authors and do not necessarily reflect those of the HTA, NIHR, NHS or the Department of Health.

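### The Aim 2 prediction model admits candidates known only after the first dislocation, chiefly rehabilitation, with no baseline cut-off, landmark or time-varying form

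*Protocol*

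**What the plan says.** Section L, under the heading on predictors of recurrent dislocations, plans a Cox model for time to re-dislocation. It uses backward selection and shrinkage, and its purpose is to identify patients at higher risk. On candidates it says "Potential risk factors will include all those described above".

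The list in question is the expert consensus table. Section K says that "this list is tabulated in Appendix E and highlights the risk factors (and covariates) deemed most important". For patients after a first dislocation, Appendix E contains "Insufficient physio / rehab after first dislocation", "Time at return to sports" and post-dislocation immobilisation. The column for patients after surgery contains "Insufficient physio / rehab after surgery" and "Time for return to sports".

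Section K does not expect every factor to be obtainable. It says the design will allow the team to "confirm through WP1 those factors that are reliably collected and that can be used for full analysis in WP2". On physiotherapy, Section F says that referral codes "will also be assessed especially in terms of data on frequency of therapy". Appendix G gives a physiotherapy code list, and question 7 of the Appendix I questionnaire asks about physiotherapy codes over the two years after the first dislocation code.

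Section L starts the outcome clock at the first dislocation and runs it for two years. Its remedy for immortal time reclassifies the period before surgery as non-surgical. It says nothing comparable about the Aim 2 predictors.

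**The concern.** Whether rehabilitation was sufficient, or when a patient returned to sport, is settled during the follow-up that the model analyses. A patient who re-dislocates in week 4 cannot finish a 12-week course. A patient who re-dislocates may also be referred for physiotherapy because of it. Either way the outcome can help to set the predictor.

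Two things are at stake. First, a model meant to identify patients at risk cannot be used at the first dislocation if some of its inputs do not yet exist; this holds whatever the size of any bias. Second, a factor with no effect may be reported as a modifiable influence on recurrence. Shrinkage and bootstrap validation deal with overfitting. They do not remove an association built into how a variable is defined, because it recurs in every resample.

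**Working it through.** **1. The text, side by side.** Candidates: everything in Appendix E (Sections K and L). Filter: reliable collection (Section K), which concerns availability and not timing. Time origin: first dislocation (Section L). Time-varying handling: surgery only (Section L). Following these statements, rehabilitation enters if its codes prove reliable. Return to sport and immobilisation have no code list and no questionnaire item, so they may never enter.

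**2. The plan's own figure.** Section G gives 656 events and N = 3065 for the surgery comparison (two-sided 5%, 90% power, 25% v 20%). Aim 2 has no figure of its own. With HR = ln 0.80 / ln 0.75 = 0.7757:

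- Schoenfeld: 4 × (1.960 + 1.282)² / (ln 0.7757)² gives 652 events.
- Freedman: (1.960 + 1.282)² × (1.7757 / 0.2243)² gives 659.
- Mean risk 22.5%, with the 10% lost contributing half their follow-up: 656 / (0.225 × 0.95) = 3069.

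The figures reproduce within 3%. They serve here only to set N and the event rate.

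**3. Share of events inside a rehabilitation course.** At constant hazard the share is [1 − (1 − 0.225)^(c/24)] / 0.225 for a course of c months. For c = 1.5 it is 7.0% (46 of 656), and for c = 3 it is 13.9% (91 of 656).

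**4. Simulation of a factor with no effect.** N = 3065, 22.5% two-year risk, full follow-up, one fixed covariate in a Cox model, two-sided p < 0.05 as the selection rule, 150 runs per setting. Assumptions not in the protocol: course length, the share who would complete it (or, in the last two rows, receive physiotherapy), hazard shape, referral after re-dislocation, and the p-value threshold.

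| Coding of the null factor | Assumption | Fitted HR | Selected |
|---|---|---|---|
| Course not completed | 1.5 months; 40/60/80% complete | 1.12 / 1.19 / 1.37 | 29 / 62 / 95% |
| Course not completed | 3 months; 40/60/80% | 1.26 / 1.41 / 1.80 | 85 / 100 / 100% |
| Course not completed | 6 months; 40/60/80% | 1.61 / 1.90 / 2.76 | 100% |
| Course not completed, front-loaded hazard (Weibull shape 0.7) | 1.5 to 6 months; 40–80% | 1.30 to 4.11 | 89–100% |
| No physiotherapy started before the event | waits up to 1.5 / 3 months; 60% | 1.09 / 1.19 | 17 / 67% |
| No physiotherapy in the whole 2 years | half of re-dislocations trigger referral; 60% | 0.42 | 100% |

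A separate run used half the sample (1,533 non-surgical patients), 25% risk and 20–50% falling short for unrelated reasons. It gave HR 1.73 to 1.30 for 12 weeks (selected in 100% to 71%) and 1.37 to 1.15 for 6 weeks (74% to 25%).

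**5. Hand check of the two directions** (60% completing or receiving physiotherapy).

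- *3-month course, not completed.* Flagged among re-dislocators: 0.4 + 0.6 × 0.139 = 0.483; among others: 0.4. Two-year risk if flagged: 0.225 × 0.483 / (0.225 × 0.483 + 0.775 × 0.4) = 26.0%. If not flagged: 0.225 × 0.517 / (0.225 × 0.517 + 0.775 × 0.6) = 20.0%. Ratio of cumulative hazards: ln 0.740 / ln 0.800 = 1.35. The Cox fit gives 1.41; the excess lies wholly in the first three months, so the two need not agree exactly.
- *Two-year window.* No physiotherapy among re-dislocators: 0.4 × 0.5 = 0.2; among others: 0.4. Risk without physiotherapy: 0.045 / 0.355 = 12.7%. With: 0.180 / 0.645 = 27.9%. Ratio: ln 0.873 / ln 0.721 = 0.41, against 0.42 simulated.

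**6. After the remedy.** With a landmark at course end or a time-varying covariate, the same null rehabilitation factor has HR 0.98 to 1.02 and is selected in about 1–9% of runs (nominal 5%, Monte Carlo error about 2 points).

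**The case against.** The case against is substantial, and much of it stands.

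- **Entry is conditional.** Section K expects some factors to be unavailable, and Sections F and J allow that physiotherapy codes may prove unreliable. If they do, the rehabilitation item drops out. This stands and limits the point. It does not answer it, because the filter never asks when a factor becomes known.
- **Reliable codes may define the control group.** Section J would then make physiotherapy referral the control definition, leaving little any-versus-none contrast among controls. This stands for the last two rows of the table. The amount of therapy could still vary, and so could rehabilitation after surgery.
- **The coding is assumed.** The protocol does not define insufficient rehabilitation, and questions 7 to 7c record physiotherapy as yes or no, not completion. This stands: the hazard ratios are illustrations. The simulation also fits one factor, without the planned multivariable selection and shrinkage.
- **Timing rules often sit in a statistical analysis plan.** Section F also promises an updated analysis plan before Work Package 2. This stands in part. A later document may set the windows, but the protocol itself fixes the candidate list, and that list contains items unknown at the time origin.

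A reader might go further and infer that Aim 2 will report too little rehabilitation as a strong risk factor, or that discrimination will be inflated. The documents do not support the first: the false association runs from small to large, and reverses under one plausible window. The second was not calculated.

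**Conclusion.** The point holds in a conditional form. As written, Section L and Appendix E admit predictors that arise after the time origin, subject only to reliable collection, and give them no timing rule. If they enter as fixed covariates, the model cannot be applied at first dislocation. That conclusion needs no simulation.

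A null factor can also be selected. For a 6- to 12-week course at constant hazard the false hazard ratio is about 1.1 to 1.8. Longer courses or early-clustered events raise it, to 4.11 in the most extreme setting tried. Milder coding gives about 1.1 to 1.2, and a full two-year window gives 0.42. All of these rest on the assumptions marked in the working, so neither a direction nor a strong effect is established. The main exposure is rehabilitation; return to sport and possibly immobilisation matter only if they are ever available. The change is worth making before Work Package 2 because it is cheap and the undefined coding alone could decide the result.

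**What to change.** In Section L, limit the Aim 2 candidates to information recorded by the prediction date: the first dislocation for the non-surgical model and the date of surgery for the surgical model. In Appendix E, flag the items that arise later.

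If rehabilitation, immobilisation or return to sport are of interest in themselves, analyse them separately. Use either time-dependent covariates or a fixed landmark in patients still event-free and under follow-up, counting only what was recorded by that date.

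The cost is a sentence in Section L and a mark in the Appendix E table. A few candidates leave the main prediction model. A landmark analysis also loses earlier events: at constant hazard, about 14% of them (91 of 656) for a 3-month landmark. Because Sections L and M draw the propensity-score covariates from the same appendix, the flag could help there too.
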